Aim 1. Maximize exercise-mediated recovery of limb muscles by using stimulation induced spinal plasticity. We will study the effect of limb training combined with Spike-Timing Dependent Plasticity (STDP) on motor function recovery. We will test the effect of three groups: (1) stimulation, (2) training +stimulation, and (3) training+sham stimulation. We hypothesize that the ability of training to promote recovery of limb motor function will be enhanced by eliciting STDP in upper and lower-limb. An important strength of this aim is the combination of training and STDP, which aims at enhancing the beneficial effects of motor training by promoting plasticity in the corticospinal pathway (Ellaway et al., 2007; Castel et al., 2009). Training effects on physiological pathways will be explored and correlated with hand/arm motor function and the site and extent of the lesion defined by structural MRI.

Aim 2. Maximize exercise-mediated recovery of limb muscles by using stimulation induced spinal plasticity. STDP has been shown to be effective in enhancing the recovery of residual limb function in humans with chronic incomplete SCI (Urbin et al., 2017). In this aim we will investigate the effect of the combination of extended STDP and training. We hypothesize the ability of training to promote recovery of motor function will be enhanced by eliciting STDP in the corticospinal pathway.

BACKGROUND:

After a SCI, many individuals present deficits in upper-limb and/or lower-limb function. Most SCIs are contusions and ~50% occur at the cervical level causing anatomically incomplete damage and bilaterally functional deficits to lower- and upper-limbs (Kakulas, 1999). Arm and leg function deficits limit daily-life activities, such as reaching and grasping, eating, writing, and walking which decreases the quality of life (Snoek et al., 2004). Regaining arm and leg function is considered the highest priority for improving the quality of life of individuals with SCI (Anderson, 2004).

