How STDP and training might contribute to recovery of upper-limb and lower-limb function: The physiological basis for these protocols comes from animal studies showing that an increase or decrease in synaptic strength can be elicited by repeated pairs of presynaptic and postsynaptic action potentials that are precisely timed with respect to each other (Bi & Poo, 1998; Dan & Poo, 1998; Bi & Poo, 2001). If antidromic stimulation of a postsynaptic cell is paired with timed orthodromic stimulation of a presynaptic cell, bidirectional plasticity can be induced (Bi & Poo, 1998; Markram et al., 1997). In humans, corticospinal neurons can be activated by transcranial magnetic stimulation (TMS), and antidromic action potentials can be elicited in sensorimotor cortex and motoneurons by peripheral nerve/ spinal cord stimulation. STDP has been used successfully to precisely pair pulses to arrive at the spinal cord (Taylor & Martin, 2009). How to strengthen synaptic plasticity in corticospinal connections targeting the spinal cord (spinal synapses) of upper-limb and lower-limb muscles after SCI combined with training and its effect on voluntary output, remains unknown and will be investigated in this study.

STUDY ENDPOINTS:

The primary outcome measure utilized in this part of study is the Graded Redefined Assessment of Strength, Sensibility and Prehension (GRASSP see below). GRASSP is an extensive and validated impairment and functional measure which is able to detect subtle neurologic changes in individuals with spinal cord injury. Specifically, it evaluates the domains of sensation, strength, quality of different grip patterns and the ability to complete a variety of functional tasks.

The primary outcome measure utilized in this part of study the 10-meter Walk test. In the group receiving lower-limb exercises, we will use the 10-meter walk test to assess walking speed in meters per second. The same percentage of body-weight support will be used during pre- and post-assessments. A stopwatch will be used to measure the time to execute the task. The 10-meter walk will be repeated 3 times and the average will be used.

Participants may complete the following secondary endpoint measurements before and after the STDP protocol as outlined below.

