If eligible, participants will be asked to complete pre, post, and follow-up assessment sessions in addition to the training sessions. Each assessment will require 2-5 sessions. Participants will complete up to 135 training sessions with a maximum of 360 paired pulses of stimulation and a small cohort of participants (n=10) will complete up to 270 training sessions with a maximum of 720 paired pulse of stimulation (up to 4 times per day). This will be determined based on preliminary data. In Aim 1, participants will be tested before and after at least 10 training sessions with single site stimulation. In Aim 2, participants will be tested before and after at least 40 training sessions with multisite stimulation. If a training session is not completed or missed participants will be asked to recover that session in a timely manner.

AIM 1: Randomized controlled design

Pre-assessment: 1. Physiology 2. Kinematics 3. Function	Stimulation Training + stimulation Training + sham stimulation	Post-assessment: 1. Physiology 2. Kinematics 3. Function	Follow-up assessment: 1. Physiology 2. Kinematics 3. Function
--	--	---	--

AIM 2:

Pre-assessment: 1. Physiology 2. Kinematics 3. Function	Training + stimulation	Post-assessment: 1. Physiology 2. Kinematics 3. Function	Follow-up assessment: 1. Physiology 2. Kinematics 3. Function
--	------------------------	---	--

We anticipate that each participant will take about 2-10 months to complete the study procedures/testing. Follow-up assessments will be done 1-9 months after completion of protocol, one follow-up in the first 3 months and the last follow-up in the 4-9 months following the last completed session. We will evaluate the subject's ability to move their hands, arms, legs, feet and/or toes using the different physiological and functional tests as mentioned above. TMS measurements, CMEPS and EMG recordings may also be done at these follow-up assessments.

INCLUSION AND EXCLUSION CRITERIA:

We anticipate the screening of 500 subjects across the two aims (60 subjects for Aim 1, and 40 for Aim 2) who have incomplete SCI at the cervical/thoracic/lumbar level (C2-L2). This number accounts for an attrition rate of 50%. To account for screen failures we would like to ask for a total of 200 subjects.

- Inclusion criteria for SCI subjects:
 - (1) Male and females between ages 18-85 years
 - (2) SCI at least 4 weeks post injury
 - (3) Spinal Cord injury at or above L2
 - (4) ASIA A,B,C, or D, complete or incomplete

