 - (5) Possess the following abilities
 - (Aim 1) The ability to produce a visible precision grip force with one hand, and/or the ability to perform some small wrist flexion and extension (Aim 2) The ability to perform a small visible contraction with dorsiflexion and hip flexor muscles

- Exclusion criteria for SCI Subjects:
 - (1) Uncontrolled medical problems including pulmonary, cardiovascular or orthopedic disease
 - (2) Any debilitating disease prior to the SCI that caused exercise intolerance
 - (3) Premorbid, ongoing major depression or psychosis, altered cognitive status
 - (4) History of head injury or stroke
 - (5) Vascular, traumatic, tumoral, infectious, or metabolic lesion of the brain, even without history of seizure, and without anticonvulsant medication
 - (6) History of seizures or epilepsy
 - (7) Receiving drugs acting primarily on the central nervous system, which lower the seizure threshold (see appendix 2)
 - (8) Pregnant females
 - (9) Ongoing cord compression or a syrinx in the spinal cord or who suffer from a spinal cord disease such as spinal stenosis, spina bifida, MS, or herniated disk
 - (10) Metal plate in skull
 - (11) Individuals with scalp shrapnel, cochlear implants, or aneurysm clips

RECRUITMENT METHODS:

We anticipate screening of 500 subjects to complete the study (see description above). We will be using the IRB approved SCI registry for recruitment. A letter granting access to the registry is included in the submission. Subjects who have previously expressed an interest in participating in research studies at the Shirley Ryan AbilityLab complete a questionnaire and request that their information be entered into the research volunteer database. This database is searchable based on criteria such as age, time-post injury and injury level. Potential subjects will be called by the study coordinator. If the individuals have not agreed to be contacted by phone for future studies then the treating physician will be the one contacting them. The phone call will be to provide information about the study to the individual to determine if they are interested in the study. We will not be collecting any information from the individual. All the screening will be done after written consent is collected and before enrollment.

COMPENSATION FOR PARTICIPATION IN RESEARCH ACTIVITIES:

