Aim 1: Repeated-measures ANOVA and Tukey post hoc analysis will determine effects of GROUP (stimulation, training+stimulation, and training+sham), TIME (before, immediately after, and follow-ups around 3 and 6 months post intervention) on physiological and behavioral outcomes. For alpha (type I error) of 0.05 and 1-beta (power) of 0.8, 45 SCI participants (15/group) will be included.

Aim 2: Repeated-measures ANOVA and Tukey post hoc analysis will determine effects training stimulation, TIME (before, immediately after, and follow-ups around 9 months post intervention) on physiological and behavioral outcomes. For alpha (type I error) of 0.05 and 1-beta (power) of 0.8, 11 SCI participants will be included.

Audio/Video Taping:

We plan to audio and video taping some parts of the experimental session, upon subject consent (optional in the consent form). Recordings will be only of the experimental activities described in the protocol. The subjects' identity will be hidden if subjects do not explicit consent to be recognized from the video or audio. The audio and video records will be stored in a password-protected file on a USB drive in a locked cabinet in the PI's office at the Rehabilitation Institute of Chicago.

The audio and video records will be used only for:

- a) Medical or scientific publications;
- b) Presentation at conferences;

The audio and video records will be destroyed after the time period chosen in the consent form.

This study does not involve any other risk to the subject, beyond some sense of effort and mild fatigue. Fatigue will be assessed based on the subjects' verbal report. They will be explicitly invited to interrupt the experiment if they experience fatigue. All studies will be carried out in the hospital environment where medical care is immediately available if needed.

POTENTIAL BENEFITS TO PARTICIPANTS:

Participation in the experiment may result in no direct improvement or, in the rare and unanticipated event, worsening of the subject's condition, including prolonged recovery time.

DATA MANAGEMENT AND CONFIDENTIALITY:

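### Aim 1 enters the pre-assessment as a level of TIME, with no baseline covariate and no named treatment test; on each reading this gives up precision that is nearly free to recover, but does not harm validity

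*Combined protocol and SAP*

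**What the plan says.** Under Statistical Analysis, Aim 1: "Repeated-measures ANOVA and Tukey post hoc analysis will determine effects of GROUP (stimulation, training+stimulation, and training+sham), TIME (before, immediately after", followed by follow-ups at about 3 and 6 months. TIME thus has four levels, the first of which is the pre-assessment. GROUP and TIME are the only effects named. No GROUP x TIME term is written, no covariate or change score appears, and the Tukey step does not say whether it compares raw means or changes. The section gives alpha 0.05, power 0.8 and 45 participants (15 per group).

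The Study Timeline labels Aim 1 a randomized controlled design. It says "In Aim 1, participants will be tested before and after at least 10 training sessions with single site stimulation", with "one follow-up in the first 3 months and the last follow-up in the 4-9 months following the last completed session". The Aim 1 hypothesis under Objectives is "We hypothesize that the ability of training to promote recovery of limb motor function will be enhanced by eliciting STDP", which points to training+stimulation versus training+sham as the main comparison.

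Study Endpoints names two primary outcomes: "The primary outcome measure utilized in this part of study is the Graded Redefined Assessment of Strength, Sensibility and Prehension", and, for the other limb, "In the group receiving lower-limb exercises, we will use the 10-meter walk test to assess walking speed in meters per second".

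**The concern.** In a randomized comparison the groups have the same expected baseline, so the pre-assessment carries no treatment effect. Its value is as a predictor of later scores. As an outcome level it is used less well: a change contrast subtracts all of it, a raw post-visit comparison ignores it, and a GROUP average over all four visits mixes a visit without any effect into the treatment estimate.

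Entry is broad ("ASIA A,B,C, or D, complete or incomplete", from four weeks after injury), so participants are likely to differ widely at baseline, although the documents give no SD. At 15 per group, the precision of the main pairwise comparison matters. Because the treatment test is not named, the size of the loss, and whether it rises or falls with r, depends on which reading the analyst adopts.

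**Working it through.** **The plan's own figure.** The 45 cannot be reproduced, because no effect size, SD, correlation or tested effect is given. Solving backwards for 80% power at N = 45, it corresponds to f = 0.38/0.42/0.44 for GROUP and 0.20/0.15/0.13 for GROUP x TIME at r = 0.5/0.7/0.8. One sample size therefore implies quite different effects depending on the unnamed test.

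**Inputs.** From the documents: 3 groups, 4 visits, 15 per group, alpha 0.05. Assumed: SD 1 at every visit, a common correlation r between visits, 15 complete cases per group, and an effect d in training+stimulation only.

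**Step 1: variance of a group contrast at one visit (per-person units).** Raw mean: 1. Change from baseline: 2(1-r). Baseline-adjusted: 1-r². Adjusted over change is (1-r)(1+r)/[2(1-r)] = (1+r)/2. Adjusted over raw is 1-r².

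| r | change | adjusted | adjusted/change | adjusted/raw |
|---|---|---|---|---|
| 0.5 | 1.00 | 0.75 | 75% | 75% |
| 0.7 | 0.60 | 0.51 | 85% | 51% |
| 0.8 | 0.40 | 0.36 | 90% | 36% |

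Estimating the slope adds about 1/(42-2) = 2.5%. After that, the adjusted contrast beats the change contrast when (1+r)/2 < 1/1.025, that is r below about 0.95. It beats the raw contrast when 1-r² < 1/1.025, that is r above about 0.16. These ratios do not depend on effect size or arm pattern, and n enters only through the slope term.

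For the mean of the three post visits, adjusted over change is [(1-r)(1+3r)/3]/[4(1-r)/3] = (1+3r)/4, or 62.5/77.5/85%.

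**Step 2: persistent effect.** Take d = 0.657/0.567/0.485, set so that an adjusted three-group test of the post mean has 80% power. With one arm shifted, the squared deviations of the group means sum to 2/3 of the squared shift, and 15 x 2/3 = 10.

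- GROUP, F(2,42): the effect is cut to 3d/4 and the variance is (1+3r)/4. Noncentrality is 10(0.75d)²/[(1+3r)/4] = 3.88/2.33/1.56; power 38/24/17%.
- Adjusted post mean, F(2,41): 10d²/[(1+2r)/3 - r²] = 10.4 at each r; power 80%.
- GROUP x TIME, F(6,126): 10(0.75d²)/(1-r) = 6.47/8.04/8.82; power 41/51/55%.
- Like-for-like adjusted 6-df test, F(6,125), with post-visit covariance given baseline (1-r)I + (r-r²)J: noncentrality 10.4; power 64%. Simulation with slope and variances estimated (20,000 runs) gives 62%.

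**Step 3: fading effects, 6-df tests** (d = 0.907/0.748/0.629 at the immediate visit).

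| Effect over post visits | Adjusted | GROUP x TIME |
|---|---|---|
| 1, 0.5, 0 | 76/78/80% | 68/75/78% |
| 1, 0, 0 | 76/80/82% | 73/79/82% |

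For the immediate-only effect at r = 0.8, simulation gives 0.818 against 0.817, so there is no practical gain.

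For GROUP, efficiency relative to the adjusted post mean is 0.75(1-r) = 37.5/22.5/15% whatever the time course. The loss grows with r, and fading does not reduce it.

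**Step 4: Tukey pair at the immediate visit, training+stimulation versus training+sham** (same d as step 3). Raw means 53/36/25%; changes 53/59/62%; adjusted 67%.

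**Type I error.** Under the null, the simulated GROUP, GROUP x TIME, adjusted 6-df and unadjusted pair tests reject in 4.9 to 5.2% of runs. The adjusted 6-df test uses a calibrated critical value; the plain F(6,125) value would give 5.5%.

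**The case against.** The strongest reply is that GROUP x TIME is the usual reading, and there the gain can be small. At r = 0.8 it is 64 against 55% for a persistent effect, 80 against 78% for the 1/0.5/0 effect and nothing for an immediate-only one. At r = 0.9 the persistent comparison is 64 against 60%. Wide, stable differences between people push r upward, towards this region. The effect sizes are also set by the adjusted test: at a persistent d = 1.06 the comparison is 98/>99/>99% against 87/99/>99%. All of this stands as a limit on size. It does not remove the gain: the documents give no r, and at r = 0.3 the persistent comparison is 64 against 32%.

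It is also fair to say that the unnamed treatment test matters more than the covariate. For a persistent effect at r = 0.8, GROUP has 17% and GROUP x TIME 55%. That is why the fix names the contrast as well as adding the covariate.

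A third reply is that moving from a 6-df test to one contrast at one time is not free. This is correct. For the 1/0.5/0 effect, an adjusted contrast on the post-visit average has 47/44/42%, against 68/75/78% for GROUP x TIME. For the persistent effect, the adjusted immediate-visit contrast has 53/57/58%, against 78% for the average. The choice of visit is a separate trade-off; only the covariate is free.

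**Conclusion.** The point holds as a nearly free improvement in precision. On each reading of the Aim 1 analysis, the pre-assessment is used less efficiently than it would be as a covariate, apart from the roughly 2.5% slope cost. At one visit, adjustment leaves 75/85/90% of the variance of a change contrast and 75/51/36% of that of a raw-mean contrast at r = 0.5/0.7/0.8.

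A reader might infer that the loss always shrinks as correlation rises or the effect fades. The first part holds only for GROUP x TIME and change contrasts, and the second only for the omnibus GROUP x TIME test. For GROUP, which is the effect that the text names, and for raw post-visit means, the loss grows with r.

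A reader might also infer bias, an inflated type I error or a wrong sample size. Randomization and the null simulations speak against the first two. Without an effect size or SD, the third cannot be judged from the documents.

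The variance ratios rest on equal variances and, for the post mean, a common correlation. The power figures also rest on the assumed effects and on 15 complete cases per group. That number is not assured: the eligibility section gives 60 for Aim 1 and 50% attrition. The number per outcome is also unclear, because the Aim 1 ability criterion concerns the hand or wrist ("The ability to produce a visible precision grip force with one hand" is one way to meet it), while Objectives covers both limbs.

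**What to change.** - For Aim 1, model the post-baseline values only, with group, visit, group x visit and the baseline value of the same measure as covariate.
- State that the treatment comparison is training+stimulation versus training+sham, estimated from this model, with Tukey-adjusted pairs.
- Fit the model separately for GRASSP and for the 10-meter walk, each in the participants trained on that limb.
- Name the target visit, or the post-visit average, before data are seen. The investigator should choose it from the expected time course, since neither option is best for every course.

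The cost is analysis wording and one degree of freedom. The pre-assessment is already collected, so no visit, measurement or participant is added.

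### Aim 1's 80% power is not tied to training+stimulation versus training+sham, the comparison its hypothesis needs, and Tukey tests that comparison with less power than one planned contrast would

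*Combined protocol and SAP*

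**What the plan says.** The Objectives section describes Aim 1 as a test of three groups: ("1) stimulation, (2) training +stimulation, and (3) training+sham stimulation". It then states the hypothesis: "We hypothesize that the ability of training to promote recovery of limb motor function will be enhanced by eliciting STDP in upper and lower-limb".

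The Statistical Analysis section gives the method for Aim 1: "Repeated-measures ANOVA and Tukey post hoc analysis will determine effects of GROUP (stimulation, training+stimulation, and training+sham), TIME". TIME has four levels: "before, immediately after, and follow-ups around 3 and 6 months post intervention". The effects are to be assessed "on physiological and behavioral outcomes". The next sentence gives alpha, power and the sample size: "For alpha (type I error) of 0.05 and 1-beta (power) of 0.8, 45 SCI participants (15/group) will be included".

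The power sentence gives no effect size, SD or within-person correlation, and it does not say which outcome, visit or comparison the 0.8 refers to. Study Endpoints names GRASSP as a primary outcome and the 10-metre walk as the primary outcome for those doing lower-limb exercise. The power sentence refers to neither.

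**The concern.** Only one pair of arms isolates what stimulation adds to training: training+stimulation against training+sham. An F test over three groups asks a broader question, whether any of the groups differ. To say which ones differ, the plan offers Tukey and nothing else. Tukey protects all three pairs equally, so it sets a stricter threshold for the one pair that the hypothesis concerns.

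A reader will naturally take 0.8 as the chance of confirming that stimulation adds to training. The plan does not show this. A real effect could give a significant GROUP test and still leave the hypothesis comparison short of the Tukey threshold.

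**Working it through.** **Inputs from the plan.** Three groups, 15 per group, alpha 0.05, power 0.8, four visits.

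**Assumptions.** Two-sided tests; 15 analysed per group; a normally distributed score (change or baseline-adjusted) with common SD; pooled error with 45 − 3 = 42 df (a baseline covariate would take one more). Differences are in SD units of that score.

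**1. Can 45 be reproduced?** No. Without an effect size and SD, it can be neither confirmed nor refuted. One can only back-solve the effect that gives 80% power at 15 per group under a chosen test.

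**2. Thresholds at 42 df.**
- Single contrast at two-sided 0.05: critical |t| = 2.018.
- Tukey, three groups: critical |t| = q/√2 = 3.436/√2 = 2.429, a per-comparison alpha of 0.0195.

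**3. Difference needed for 80% power.** For a true difference of d SD, the statistic is noncentral t with noncentrality d·√(15/2) = 2.739·d.
- Single contrast: 80% at d = 1.05 (noncentrality 2.88).
- Tukey: 80% at d = 1.20 (noncentrality 3.29).
- At d = 1.05, Tukey has 67%.

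**4. Power for training+stimulation versus training+sham under possible origins of 45.** The omnibus F (2 and 42 df) has 80% power at f = 0.480. With one training arm differing from two equal groups, d = 3f/√2 = 1.02. With evenly spaced means, the extremes differ by √6·f = 1.175 and neighbours by half of that, 0.59.

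| Assumed origin of 45 | d | Tukey | Single contrast at 0.05 |
|---|---|---|---|
| Two-sample t test | 1.06 | 68% | 81% |
| Omnibus F, one training arm differing | 1.02 | 64% | 78% |
| Omnibus F, even spacing, training arms at the extremes | 1.175 | 78% | 88% |
| Omnibus F, even spacing, training arms adjacent | 0.59 | 22% | 35% |
| Tukey comparison itself | 1.20 | 80% | 89% |

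The single contrast gains about 9 to 14 points in every row.

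**5. Four-visit design.** Suppose instead that 45 came from the GROUP-by-TIME interaction (6 and 126 df) with a sustained effect. Tukey power is then:
- one arm differing: 60% on immediate post minus pre, 80% on mean post minus pre;
- even spacing, training arms at the extremes: 74% and 91%;
- even spacing, training arms adjacent: 20% and 31%.

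Across steps 4 and 5 the range is about 20% to 91%.

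**6. Where 1.05 SD does not apply.**
- Omnibus F as a gate, then unadjusted pairwise tests: at d = 1.05, simulation (200,000 trials) gives 76% with one arm differing and 69% with even spacing and the training arms at the extremes.
- GROUP effect averaged over all four visits, baseline included: a sustained post-treatment effect of 1.05 SD shrinks to 0.75 × 1.05 = 0.79. The SD of a four-visit mean is √((1 + 3ρ)/4), which is 0.79 at ρ = 0.5 and 0.92 at ρ = 0.8 (assumed values). The standardised effects are 1.00 and 0.85, with power 76% and 63%.

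**7. Does testing the hypothesis pair first control error?** If that pair is truly equal, a false claim requires rejecting it, which has probability 0.05. If it truly differs, at most one of the other two equalities can be true, so testing both at 0.05 adds at most 0.05. Familywise error therefore stays at 0.05 for one outcome at one visit.

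**The case against.** ANOVA followed by Tukey is a standard and valid way to compare three groups, and Aim 1 does say that three groups will be tested. The plan does not attach the 0.8 to any particular test and gives no rule making Tukey decisive; both are inferences from adjacent sentences. The planned model has four visits, whereas most of the working above concerns a single score per person.

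Much of this stands. In particular, a reader might infer from the first two rows of the table that Aim 1 has only 64% to 68% power. The documents do not support that. Those figures follow from two assumed derivations, and other admissible ones give anything from about 20% to 91%, including 80% if 45 was derived for Tukey. In the row with one arm differing, part of the shortfall also comes from moving from an F test to a pairwise test: the unadjusted contrast has 78%, not 80%.

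A reader might also infer that with three groups Tukey can simply be dropped after a significant F and 80% claimed at 1.05 SD. Step 6 shows that this is wrong for power, although the gate does hold familywise error at 0.05 for one outcome at one visit.

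What the objection does not remove is the comparison of thresholds. For the same effect on the same contrast, 2.429 is harder to exceed than 2.018, whatever lay behind 45. Nor does the plan offer any other route to the pairwise answer that its hypothesis needs.

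**Conclusion.** The point holds in a limited form. The stated 80% cannot be checked or interpreted, because the outcome, visit, contrast, effect size and SD are all absent. The planned pairwise method is also less powerful than it need be for the one comparison in the hypothesis. With 15 analysed per group, the difference detectable with 80% power is about 1.20 SD under Tukey and 1.05 SD for a single contrast. At the effects examined, the single contrast gains about 9 to 14 percentage points. This rests on a two-sided test, a normal score with common SD and 42 error df.

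It is not shown that the trial is underpowered, or that its Tukey power is any particular figure. Nor is it shown that 45 is enough: the eligibility section gives 60 subjects for Aim 1 and 50% attrition, and 15 analysed per group is taken here as given. This is a worthwhile improvement to the analysis plan, not an error that invalidates it.

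**What to change.** In the Aim 1 paragraph of Statistical Analysis:

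- Name training+stimulation versus training+sham as the first comparison. Define it as change from baseline, or a baseline-adjusted score, on the stated primary outcome at the immediate post-intervention assessment. Say which of the two primary outcomes it uses.
- Test it two-sided at 0.05. Test the other two pairs, each at 0.05, only if it is significant.
- Restate the power sentence: 15 analysed per group give 80% power for a difference of about 1.05 SD of that change or adjusted score (about 1.20 SD if Tukey is kept). Express that difference in the outcome's own units, with a source for the SD.
- State that familywise control covers one outcome at one visit. Other visits and outcomes are supportive unless given their own rule.
- Do not attach the 1.05 SD figure to an F-gated procedure or to a GROUP effect averaged over visits that include baseline.

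The cost is a change of wording, with no participants or data added by this change. The one real loss is that comparisons with stimulation alone are confirmatory only if the first contrast succeeds. The restated sentence will also make plain that the detectable difference is large, at about one SD.
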